## 10. TREATMENT

### 10.1. Randomisation options

Patients will be eligible for entry into one of the following randomisation options according to:

- boost volume (whether the tumour volume identified on the staging MRI is suitable for focal boost or not),
- suitability and availability of HDR (e.g. patient not suitable for HDR brachytherapy or any other clinical reason) and,
- type of focal boost (IMRT or HDR brachytherapy).
- Suitability and availability of focal IMRT boost.

In centres with no access to HDR or focal IMRT boost, all patients will enter randomisation option 1 (irrespective of having a suitable boost or not). Randomisation option 1 closed to recruitment on 1st April 2022

**Randomisation Option 1 (Pelvic node randomisation):** No suitable focal boost volume on the staging MRI\* and not suitable for HDR brachytherapy:

Arm	Radiotherapy treatment area	
	Prostate dose	Pelvic node dose
A	60Gy/20#	
B	60Gy/20#	47Gy/20#

*\*this includes patients with post-biopsy MRI and patients with pre-biopsy MRI not fulfilling conditions for suitable boost*

**Randomisation Option 2a (Pelvic node and whole gland boost):** No suitable focal boost volume on the staging MRI\* and suitable for HDR:

Arm	Radiotherapy treatment area		
	Prostate dose	Pelvic node dose	Whole gland HDR
A	60Gy/20#		
B**	60Gy/20#	47Gy/20#	
C1	37.5Gy/15#		15Gy/1#
D1	42Gy/20#	47Gy/20#	15Gy/1#

*\*this includes patients with post-biopsy MRI and patients with pre-biopsy MRI not fulfilling conditions for suitable boost.*

*\*this also includes patients who have a suitable boost volume on MRI at a HDR centre where only **whole gland HDR** is RTQA is approved.*

*\*\*Arm B closed to recruitment in Q2 2022*

**Randomisation Option 2b (Pelvic node and focal boost randomisation):** Suitable focal boost volume

[figure not shown]
Arm	Radiotherapy treatment area			
	Prostate dose	Pelvic node dose	Focal Boost dose	
			Focal IMRT**	Focal HDR**
A	60Gy/20#			
B***	60Gy/20#	47Gy/20#		
C2	60Gy/20#		67Gy/20#	
C2	37.5Gy/15#			15Gy/1# (whole prostate) 19Gy/1# (tumour boost dose)
D2	60Gy/20#	47Gy/20#	67Gy/20#	
D2	42Gy/20#	47Gy/20#		15Gy/1# (whole prostate) 19Gy/1# (tumour boost dose)

*\*\* use of focal HDR or focal boost IMRT determined for each patient prior to randomisation.*

See figure 1 (next page) for the decision algorithm to determine what randomisation option corresponds to each patient.

*\*\*\* Arm B closed to recruitment in Q2 2022*

Figure 1. Decision tree algorithm to allocate a patient into the appropriate randomisation option

## **10.2. Treatment timelines**

Radiotherapy treatment should commence ideally within 8 weeks following randomisation and within 6 months of starting hormone therapy (see 10.3). Delays to radiotherapy (with extended ADT) due to COVID19 clinical management strategies are permitted and should be documented (details of how to do this are given in the Trial Guidance notes).

## **10.3. Hormone therapy**

Hormone therapy (ADT) will typically commence after completion of the staging investigations. If choline PET CT scans or PSMA PET CT scans are used for assessment, these should be arranged prior to commencement of ADT.

Patients in the intermediate risk group will receive 6 -12 months of ADT, and patients in the high risk group may receive 2-3 years of ADT; patients undergo planning ideally after 2-4 months (maximum 6) of neo-adjuvant ADT and commence radiotherapy at a maximum of 6 months.

For patients affected by the COVID-19 pandemic, there is no restriction on length of time patients can be on ADT prior to randomisation, however the duration of ADT must be less than 12 months prior to radiotherapy starting .

LHRH antagonists or LHRH agonists with short-term androgen blockade are standard of care; bicalutamide daily or cyproterone acetate for 1 to 2 weeks is given initially to prevent possible 'tumour flare' phenomenon. ADT is part of routine care; therefore drugs will be provided by standard local arrangements.

Bicalutamide monotherapy can be used if patients have significant cardiovascular co-morbidity or wish to maintain sexually active. Troublesome gynaecomastia or breast pain should be treated with radiotherapy to the breast tissue or tamoxifen may be given.

## **10.4. Image guided radiotherapy**

Daily imaging and online correction (kV, CBCT, CT on rails, tomotherapy or MR-guided RT) are mandatory for all arms. Fiducial markers or soft tissue imaging can be used for IGRT. For fiducial marker insertion a minimum of three fiducial markers are inserted into the prostate as per standard care. Markers should ideally be separated 20mm apart. This can be undertaken before the HDR implant if appropriate, depending on the type of marker, an appropriate time prior to external beam planning should be scheduled.

## **10.5. Radiotherapy planning and delivery**

All participants will be planned to receive 15 or 20 fractions of radiotherapy delivered daily. External beam radiotherapy planning will ideally be performed during month 2-4 (maximum 6) of ADT and radiotherapy treatment will commence within 6 months of ADT. Delays to radiotherapy (with extended ADT) due to COVID19 clinical management strategies are permitted and should be documented (details of how to do this are given in the Trial Guidance Notes).

If participants are allocated to a HDR implant, the HDR implant will be scheduled 14-21 days before starting EBRT (EBRT will consist of 15 fractions for arm C1 or C2 and 20 fractions for arm D1 or D2). EBRT planning will be carried out before or after the HDR implant. EBRT is started two to three weeks after the HDR (day 0). However, if it is standard protocol in the unit, HDR implant can be scheduled 2-3 weeks after completion of EBRT subject to RTQA approval. The first acute toxicity assessment occurs during week 1 of EBRT.

Radiotherapy planning and outlining should be carried out in accordance with the guidelines in the current version of the radiotherapy planning and delivery guidelines, available in the PIVOTALboost site investigator file and on request from ICR-CTSU ([contact]).

#### **10.6. EBRT treatment scheduling and gaps**

Treatment can start on any day of the week other than a Monday and is given daily, 5 fractions per week; overall duration should be 28-33 days. A gap of up to 5 days is acceptable in the event of machine service, breakdown or re-planning but further delays should be avoided. Patients should not be started prior to a bank holiday period if this would prolong treatment for more than 7 days. If there is a delay for more than 5 days, please add details including the length of overall treatment time and the reason (radiotherapy toxicity, intercurrent illness, technical issues related to radiotherapy delivery, technical issues related to patient factors e.g. re-planning) on the CRF.

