**C: Prostate IMRT & prostate boost**

**D: Prostate & pelvic IMRT & prostate boost**

**RT treatment (4 weeks):**

Acute toxicity (RTOG) weekly during RT and weeks 6, 8, 12, 18

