## **8.3. On-treatment assessments**

- Acute toxicity assessment (RTOG, CTCAE v.4) weekly during treatment
- IPSS (at the end of week 4 of treatment).

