## 9. SCHEDULE OF ASSESSMENTS

Visit/Assessment	Screening (pre-randomisation)	Pre-treatment	External beam treatment week 1-4	Week 6, 8, 12	Week 18	6, 12, 18, 24, 36, 48, 60 months	Annually thereafter	PSA failure or disease recurrence
Histological confirmation of prostate cancer	X							
Complete history and physical examination (physical examination & DRE if clinically indicated)	X							
WHO PS, ASA score, ACE-27 score	X							
Radiological assessment (multi-parametric MRI scan, and one of the following: bone scan, WB MRI, MRI spine, Choline PET, PSMA PET)	X 							
PSA	X	X 				X	X	X
FBC, U+E	X							
Testosterone		X 						
Clotting and ECG		X 						
Baseline signs & symptoms (RTOG, CTCAE v.4)	X	X						
Acute toxicity assessment (RTOG, CTCAE v.4)		X	X	X	X			
QL questionnaires – IPSS	X		X 	X	X			
QL questionnaires – EPIC & EQ-5D	X				X	X		
QL questionnaires – ALERT-B, GSRs, IIEF-5 (SHIM)	X					X		
Late toxicity assessment (RTOG, CTCAE v.4)						X	X	
Assessment of disease status						X	X	X

Screening radiological assessment should take place ideally within 2 months and within a maximum of 12 months prior to randomisation AND no more than 6 months prior to starting ADT. For details how patients are screened and assessed during the COVID pandemic, please refer to section 8.1 and 8.2

Only for patients randomised to HDR.

IPSS questionnaire to be completed only at the end of week 4.

at least 2 months after starting ADT and prior to starting radiotherapy. For patients who have had multiple PSAs whilst on ADT, prior to starting radiotherapy, please record the one closest to the radiotherapy start date.

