### **13.7. Interim analyses and stopping rules**

Adherence to dose volume constraints will be checked after 30 patients are recruited to each experimental arm to ensure treatment can be delivered within safe constraints. Adherence to treatment will be monitored closely during recruitment: in particular any delays or interruptions of more than 5 days of treatment will be escalated to the Trial Management Group.

The IDMC will review emerging safety and efficacy data at regular intervals (at least annually).

Once 119 patients have been recruited to each of the experimental arms (B, C, and D) and completed their week 18 toxicity assessment an interim safety analysis will be conducted to rule out 30% (or more) patients with RTOG grade 2 or worse bladder or bowel complications. The figure has been estimated assuming an expected rate of 20% in the control group (inferred from data for all patients in the PIVOTAL study) and powered (80% power, 0.05 one-sided  $\alpha$ ) with a one-stage A'Hern design. If 27 or more patients out of 119 in one group developed bladder or bowel complications of grade 2 or more at 18 weeks, consideration will be given to modifying the trial design by dropping the treatment arm. As the recruitment pattern for arm B is different to arms C and D this analysis will be carried out as the data for each of the experimental arms matures.

No formal early stopping rule for futility or efficacy for the primary endpoint (FFS) has been planned.

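### Section 10.6 sets one EBRT duration, 28-33 days, that fits only 20 fractions; the 15-fraction HDR courses in arm C take 21-26 days and fall below it when given as prescribed

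*Protocol*

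**What the plan says.** Section 10.6 has treatment given five days a week, starting on any day but Monday, and adds that "overall duration should be 28-33 days". It then says "A gap of up to 5 days is acceptable" for machine service, breakdown or re-planning, and asks for the reason on the CRF if a delay exceeds 5 days. Section 13.7 adds that "any delays or interruptions of more than 5 days of treatment will be escalated to the Trial Management Group".

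The number of fractions is not the same for everyone. For patients having an HDR implant, section 10.5 says "EBRT will consist of 15 fractions for arm C1 or C2 and 20 fractions for arm D1 or D2". The tables in section 10.1 agree: C1 and the HDR form of C2 are 37.5Gy in 15 fractions. The focal IMRT form of C2, and all of A, B and D, have 20 fractions.

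The on-treatment visits are described in two ways. The schema, under a heading of four weeks of treatment, has "Acute toxicity (RTOG) weekly during RT and weeks 6, 8, 12, 18", and section 8.3 likewise asks for weekly toxicity assessment during treatment, plus "IPSS (at the end of week 4 of treatment"). The column in section 9 is "External beam treatment week 1-4" for all patients, and the trial summary also gives weeks 1-4. Section 13.6 summarises acute toxicity at each time point and as the worst grade during radiotherapy.

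**The concern.** A delivery rule should be one that correctly given treatment can meet. Here a 15-fraction course that follows sections 10.1, 10.5 and 10.6 in every other respect lies outside the stated duration. Anyone checking adherence against 10.6 would find every undelayed HDR course in arm C out of range.

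The same four-week assumption appears in the visit wording. If on-treatment assessment stops with the last fraction, an arm C patient treated with HDR is observed for a shorter on-treatment period than a patient in arm A. The worst-toxicity summary in 13.6 could then cover unequal time in arms that are to be compared. The primary objective asks for better disease control with similar bladder and bowel side effects, so equal windows are worth fixing in the text.

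**Working it through.** **Inputs.** Five fractions a week, no Monday start, gap of up to 5 days, stated range 28-33 days (section 10.6). Fraction numbers 15 and 20 (sections 10.1 and 10.5). HDR implant 14-21 days before EBRT in the usual sequence (section 10.5).

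**Formula.** Let n be a multiple of 5, with one fraction per weekday and a start on Tuesday to Friday. The last fraction falls n/5 weeks on, on the weekday before the starting weekday. Counted inclusively, the course takes 7 × n/5 calendar days. The longest accepted course adds 5 days.

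**The plan's own figure.** For n = 20: 7 × 4 = 28 days, and 28 + 5 = 33. This reproduces 28-33 exactly, from every permitted start day.

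**The 15-fraction course.** For n = 15: 7 × 3 = 21 days, and 21 + 5 = 26.

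| Course | No gap | With 5-day gap | Shortfall against 28 days |
|---|---|---|---|
| 20 fractions | 28 | 33 | none |
| 15 fractions | 21 | 26 | 28 − 21 = 7; 28 − 26 = 2 |

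**Other readings tried.**
- Gap counted as five lost weekdays: 20 fractions take 35 days, above the printed 33, so this is not how the range was built. Fifteen fractions would reach 28 days only with the full gap; an undelayed course is still 21.
- Implant counted in the duration: 14 + 21 = 35 to 21 + 21 = 42 days for 15 fractions, and 14 + 28 = 42 to 21 + 28 = 49 for 20. Neither gives 28-33.
- Monday start, which is barred: 19 days for 15 fractions and 26 for 20.

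No reading brings an undelayed 15-fraction course into range.

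**Visit window.** Sections 8.4.1 and 8.4.2 count later visits from the first EBRT fraction. Counted that way in 7-day weeks, 15 fractions end on day 21 and 20 fractions on day 28. Weekly assessment during treatment then gives three visits with 15 fractions; the section 9 column gives four. The literal span of radiotherapy is 21 days in arm C with HDR and 28 days in arm A.

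**The case against.** The strongest reply is that nothing follows from the error. The duration is worded as a target. The CRF and Trial Management Group triggers act on delay, not total duration, so they do not misfire on a short course. The fraction number is explicit in sections 10.1 and 10.5. All of this stands, and it limits the weight of the point. It does not make the printed range correct for 15 fractions.

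Four stronger readings are tempting, and the documents do not support them.

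- *The rule invites sites to stretch 15 fractions to 28 days.* Section 10.6 itself says that further delays should be avoided. Nor is it settled that the 7-day stretch needed would breach every limit. It exceeds a 5-day gap in calendar days, but a lost week is five treatment days, and 10.6 accepts up to 7 days of bank-holiday prolongation.
- *These patients have no week 4.* That holds only in 7-day weeks from the first fraction. With Monday starts barred, a 15-fraction course touches four calendar weeks (for example 4 + 5 + 5 + 1 fractions from a Tuesday). On that count 20 fractions touch five, so the calendar reading is not decisive either. Section 9 and the trial summary already set weeks 1-4 for everyone, and the section 9 footnote puts the IPSS at the end of week 4 without tying it to treatment.
- *The toxicity comparison is biased.* Section 12.5 has each form record the highest grade since the last visit, so toxicity after day 21 is still captured by week 6, and 13.6 reports every time point. The exact window for the worst-grade summary may be settled in the SAP, which is not shown.
- *The duration error also bears on late implants.* Section 10.5 says that the "HDR implant can be scheduled 2-3 weeks after completion of EBRT subject to RTQA approval". This is a separate sequencing exception, open to HDR patients in arm D too, and visits to week 18 follow it. It is no part of this point.

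**Conclusion.** The duration rule in section 10.6 is wrong for the 15-fraction HDR courses in arm C. Their accepted range, 21-26 days, lies wholly below the stated minimum of 28, by 7 days as prescribed and by 2 days with the full gap. This assumes weekday delivery, a Tuesday-to-Friday start, inclusive counting and a gap in calendar days; these assumptions reproduce the printed range for 20 fractions. An undelayed course stays out of range under every alternative tried.

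The differences in visit wording and the possible 21- against 28-day window are minor ambiguities from the same cause. The HDR share of arm C is not given, so no size of effect can be derived and none is claimed. The delay triggers, failure-free survival, the week-18 toxicity endpoint and the week-18 safety rule are unaffected.

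**What to change.** In section 10.6, state 28-33 days for 20 fractions and 21-26 days for 15 fractions.

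As a minor alignment, make section 8.3 and the schema match section 9: toxicity in weeks 1, 2, 3 and 4, and the IPSS at the end of week 4, counted from the first EBRT fraction for every patient whatever the number of fractions. In section 13.6, take the worst on-treatment toxicity over the same weeks 1-4 in all arms, so that arm C with HDR and arm A are compared over equal time. The week-4 IPSS will then fall 28 − 21 = 7 days after the last fraction of an undelayed 15-fraction course and on the day of the last fraction of an undelayed 20-fraction course. That follows from the regimens and can be noted when reporting.

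The cost is a few words in four places and, at sites that now stop at week 3, at most one further assessment per 15-fraction patient. For patients already treated without a week-4 form, the week-6 form covers the interval.

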#### **10.7. Supportive care guidelines**

In the event of patient catheterisation during the course of treatment it is expected that the participant will continue and complete radiotherapy in accordance with their allocated treatment group. As the bladder requires filling prior to treatment delivery, the catheter must be clamped or a flip-valve is used.

Participants' symptoms should be managed according to local practice, although the following are suggestions for patient care:

- Slow flow and frequency: tamsulosin or alfuzosin are often helpful.
- Dysuria/Frequency: Check for evidence of infection and treat if present with appropriate antibiotics, anticholinergics (eg oxybutynin, tolterodine, solifenacin), NSAIDs, analgesics.
- Diarrhoea: Loperamide or opioid
- Proctitis: suppository +/- local anaesthetics (e.g. sheriproct, proctosedyl)

#### **10.8. Concomitant therapy**

All medication considered necessary for the patients' welfare and which is not expected to interfere with the evaluation of the treatment may be given at the discretion of the investigator. All concomitant medications (including start/stop dates, dose frequency, route of administration and indication), must be recorded in the patient's notes, and if applicable also on the appropriate pages of the CRF.

#### **10.9. Non-permissible medications/therapies**

Non-permissible concurrent medications/therapies include:

- Adjuvant chemotherapy is not considered standard of care in this patient population as per NHS guidance.

### **11. RADIOTHERAPY QUALITY ASSURANCE (QA)**

A comprehensive QA programme for the PIVOTALboost trial will be designed and implemented by the NCRI Radiotherapy Clinical Trials Quality Assurance (NCRI RTTQA) group. This will include pre-trial and on-trial components and full details are provided in the Radiotherapy Planning and Delivery Guidelines document.

#### **11.1. Pre-trial quality assurance programme**

The following will need to be completed by participating centres prior to site activation.

1. Facility questionnaire
2. Benchmark outlining cases
3. Benchmark planning cases
4. MRI QA questionnaire

### **11.2. On-trial quality assurance programme**

On-trial QA may be streamlined with previous pelvic trials, to be advised by the RTQA team on a site-by-site basis, and includes:

1. Prospective and/or retrospective case reviews
2. Collection of staging MRI imaging
3. Review of HDR implant parameters (see RTQA document for details)
4. Dosimetry site visit (subject to prior RTQA dosimetry accreditation)
5. DICOM data collection for all patients

## **12. SAFETY REPORTING**

### **12.1. Adverse event (AE)**

Any untoward medical occurrence in a patient or clinical trial subject administered a research procedure; events do not necessarily have a causal relationship with the procedure.

### **12.2. Serious adverse event (SAE)**

An SAE is any untoward medical occurrence that occurs after the commencement of study treatment (including fiducial marker/HDR implant ) and within 30 days of the last treatment administration and:

- results in death;
- is life-threatening;
- requires hospitalisation or prolongation of existing hospitalisation;
- results in persistent or significant disability or incapacity;
- consists of a congenital anomaly or birth defect; or
- is otherwise considered medically significant by the investigator.
- Additionally, RTOG Grade $\geq$ 3 acute or late radiation side effects i.e. related to study treatment, occurring within 5 years after radiotherapy treatment will be regarded as an SAE.

Important adverse events that are not immediately life-threatening or do not result in death or hospitalisation, but may jeopardise the subject or require intervention to prevent one of the other outcomes listed in the definition above, may also be considered serious.

Progression of the indicated disease and death due to progression of prostate cancer are not considered SAEs.

Pregnancy or aid in the conception of a child whilst participating in a trial is not itself considered an SAE but should be followed up for congenital anomalies.

### **12.3. Serious Adverse Reaction (SAR)**

A serious adverse reaction is an SAE that is suspected as having a causal relationship to the research procedure, as assessed by the investigator responsible for the care of the patient. A suspected causal

relationship is defined as possibly, probably or definitely related (see definitions of causality table).  
Definitions of causality:

Relationship	Description
Unrelated	There is no evidence of any causal relationship with the trial procedure
Unlikely	There is little evidence to suggest there is a causal relationship (e.g. the event did not occur within a reasonable time after the trial procedure. There is another reasonable explanation for the event (e.g. the patient's clinical condition, other concomitant treatment)
Possible	There is some evidence to suggest a causal relationship (e.g. because the event occurs within a reasonable time after the trial procedure. However, the influence of other factors may have contributed to the event (e.g. the patient's clinical condition, other concomitant treatments)
Probable	There is evidence to suggest a causal relationship, and the influence of other factors is unlikely
Definitely	There is clear evidence to suggest a causal relationship, and other possible contributing factors can be ruled out
Not assessable	There is insufficient or incomplete evidence to make a clinical judgement of the causal relationship.

#### 12.4. Related Unexpected Serious Adverse Event

An adverse event that meets the definition of serious and is assessed by the CI or nominative representative as:

- "Related" – that is, it resulted from administration of any of the research procedures, and
- "Unexpected" – that is, the type of event is not listed in the protocol as an expected occurrence (see section 12.7)

